### 6.2.2.3 Dose Selection and Timing

Subjects in Groups 1 and 2 (Mexico) will receive Prevnar 13® administered at 2, 4, 6, and 12 months of age.

Subjects in Groups 3 and 4 (the Russian Federation) will receive Prevnar 13®a administered at 2 and 4.5 months of age.

### 6.2.3 Identity of Other Product 4

**Hexacima® (DTaP-IPV-HB-Hib):** Diphtheria, tetanus, pertussis (acellular, component), hepatitis B (recombinant deoxyribonucleic acid [rDNA]), poliomyelitis (inactivated), and *Haemophilus influenzae* type b conjugate vaccine (adsorbed) (Sanofi Pasteur SA, Lyon, France); (licensed in Mexico as Hexacima®)

**Form:** Suspension for injection

**Dose:** 0.5 mL

**Route:** IM

**Batch number:** To be determined

#### 6.2.3.1 Composition

Each 0.5 mL dose is formulated to contain the following components:

Diphtheria Toxoid .....  $\geq$  20 international units (IU)

Tetanus Toxoid .....  $\geq$  40 IU

*Bordetella pertussis* antigens

Pertussis Toxoid.....25  $\mu$ g

Filamentous Haemagglutinin..... 25  $\mu$ g

Poliovirus (Inactivated)

Type 1 (Mahoney)..... 40 D antigen units

Type 2 (MEF-1) ..... 8 D antigen units

Type 3 (Saukett).....32 D antigen units

Hepatitis B surface antigen ..... 10  $\mu$ g

---

a No endpoints will be measured for this vaccine, as it is considered out of scope for this study

*Haemophilus influenzae* type b polysaccharide .....12 µg  
(Polyribosylribitol Phosphate) conjugated to Tetanus Protein.....22-36 µg

The vaccine also contains the excipients: disodium hydrogen phosphate, potassium dihydrogen phosphate, trometamol, saccharose, essential amino acids including L-phenylalanine, and water for injections. The vaccine may contain traces of glutaraldehyde, formaldehyde, neomycin, streptomycin, and polymyxin B, which are used during the manufacturing process.

### 6.2.3.2 Preparation and Administration

Hexacima® is supplied as a suspension for IM injection in 0.5 mL single-dose prefilled syringes. Prior to administration, all study products must be inspected visually for cracks, broken seals, correct label content, and extraneous particulate matter and / or discoloration, whenever solution and container permit. If any of these conditions exists, the vaccine must not be administered. Another dose is to be used, and the event is to be reported to the Sponsor. One dose (0.5 mL) of Hexacima® will be administered IM into the anterolateral area of the thigh or the deltoid muscle of the arm, as per local country preferences, the Investigator's criteria, and depending upon the number of vaccinations received. The site of injection should be documented. The site of injection should be prepared with a suitable antiseptic. After administration of the vaccine, the used syringe and needle will be disposed of in accordance with currently established guidelines. Subjects must be kept under observation for 30 minutes after vaccination under the supervision of a responsible healthcare professional at each study site to ensure their safety, and any reactions during this period will be documented in the CRF. Appropriate medical equipment and emergency medications, including epinephrine (1:1000), must be available on site in the event of an anaphylactic or other immediate allergic reaction.

The procedures for preparing and administering Hexacima® are detailed in the Package Insert.

### 6.2.3.3 Dose Selection and Timing

All subjects in Groups 1 and 2 (Mexico) will receive a total of 4 doses of Hexacima®, administered at 2, 4, 6, and 12 months of age.

### 6.2.4 Identity of other product 5

**Pentaxim®**: (Diphtheria, Tetanus, Pertussis (Acellular, Component) Poliomyelitis (inactivated) Vaccine, (Adsorbed) and *Haemophilus influenzae* type b Conjugate Vaccine (Sanofi Pasteur S.A., France).

**Form:** Powder and suspension for injection.

**Dose:** 0.5 mL

**Route:** IM

**Batch number:** TBD

#### 6.2.4.1 Composition

Each 0.5 mL dose contains, after reconstitution:

Diphtheria Toxoid ..... ≥ 30 IU

Tetanus toxoid ..... ≥ 40 IU

*Bordetella pertussis* antigens:

Toxoid (PT) ..... 25 µg

Filamentous hemagglutinin (FHA)..... 25µg

Poliomyelitis virus:

Type 1 ..... 40 D-antigen units (DU)

Type 2 ..... 8 DU

Type 3 ..... 32 DU

Polysaccharide of *Haemophilus influenzae type b conjugated to tetanus protein* ..... 10 µg

Tetanus toxoid (PRP-T)..... 24 µg

Excipients:

Saccharose, trometamol, aluminium hydroxide. Hanks' medium without phenol red, acetic acid and / or sodium hydroxide for pH adjustment, formaldehyde, phenoxyethanol, water for injections

#### 6.2.4.2 Preparation and Administration

Pentaxim® is supplied as a powder and suspension for injection.

See the Pentaxim® package insert (44) for precautions and the procedure for preparing and administering Pentaxim®.

Each 0.5 mL dose is to be injected IM into the anterolateral area of the thigh.

The site of injection should be documented. The site of injection should be prepared with a suitable antiseptic. After administration of the vaccine, the used syringe and needle will be disposed of in accordance with currently established guidelines.

#### 6.2.4.3 Dose Selection and Timing

Subjects in Groups 3 and 4 (the Russian Federation) will receive Pentaxim® administered at 3, 4.5, and 6 months of age.

#### 6.2.5 Identity of Other Product 6

**ENGERIX-B®**: (Hepatitis B Vaccine [Recombinant]) (GlaxoSmithKline Biologicals 441 Rixensart, Belgium)

**Form:** Suspension for injection

**Dose:** 0.5 mL

**Route:** IM

**Batch number:** TBD

### 6.2.5.1 Composition

Each 0.5 mL pediatric/adolescent dose contains 10 µg of hepatitis B virus surface antigen adsorbed on 0.25 mg aluminum as aluminum hydroxide.

Excipients:

Sodium chloride.....	9 mg/mL
Disodium phosphate dihydrate.....	0.98 mg/mL
Sodium dihydrogen phosphate dihydrate.....	0.71 mg/mL

### 6.2.5.2 Preparation and Administration

ENGERIX-B® is supplied as 0.5 mL prefilled syringes.

See the ENGERIX-B® package insert (45) for specific precautions and the procedure for preparing and administering ENGERIX-B®.

Each 5 mL dose is to be injected IM middle third of the anterolateral thigh region. The site of injection should be documented. The site of injection should be prepared with a suitable antiseptic. After administration of the vaccine, the used syringe and needle will be disposed of in accordance with currently established guidelines.

### 6.2.5.3 Dose Selection and Timing

Subjects in Groups 3 and 4 (the Russian Federation) will receive ENGERIX-B® administered at 6 months of age.

### 6.2.6 Identity of Other Product 7

**RotaTeq®**: (Rotavirus Vaccine, Live, Oral, Pentavalent) (Merck Sharp & Dohme Corp., a subsidiary of Merck & Co., Inc., Whitehouse Station, NJ, USA)

**Form:** Oral solution

**Dose:** 2 mL

**Route:** PO

**Batch number:** TBD

#### 6.2.6.1 Composition

Each 2 mL dose contains the following 5 live reassortant rotaviruses:

G1 serotype.....	2.2 x 10  infectious units
G2 serotype.....	2.8 x 10  infectious units
G3 serotype.....	2.2 x 10  infectious units
G4 serotype.....	2.0 x 10  infectious units
P1A(8) .....	2.3 x 10  infectious units

The reassortants are suspended in a buffered stabilizer solution.

Each 2 mL vaccine dose also contains sucrose, sodium citrate, sodium phosphate monobasic monohydrate, sodium hydroxide, polysorbate 80, cell culture media, and trace amounts of fetal bovine serum.

#### **6.2.6.2 Preparation and Administration**

RotaTeq® is supplied in a container consisting of a squeezable plastic dosing tube with a twist-off cap, allowing for direct PO administration.

See the RotaTeq® package insert (46) for specific precautions and for the procedure for preparing and administering RotaTeq®.

Each 2 mL dose is to be administered PO, according to the instructions in the package insert.

#### **6.2.6.3 Dose Selection and Timing**

Subjects in Groups 1 and 2 (Mexico) will receive RotaTeq® administered at 2, 4, and 6 months of age.

### **6.3 Product Logistics**

#### **6.3.1 Labeling and Packaging**

MenACYW conjugate vaccine and Menveo® will be supplied by the Sponsor and will be labeled and packaged in cartons, according to national regulations. The content of the label, and the language in which it is written, will also be in accordance with the local regulatory specifications and requirements. Each carton will have 2 detachable labels to enable identification of the Investigational Products and provide information on the study. The detachable carton labels may be affixed to source documents and the subject's vaccination card. See the Operating Guidelines for additional details.

All other vaccine products will be packaged and labeled according to the regulations of each country. Where permitted by national laws and regulations, the remaining vaccine products will retain their original commercial labels and packaging. Additional labels will be applied, as necessary, in the appropriate language, according to national laws and regulations.

#### **6.3.2 Product Shipment, Storage, and Accountability**

##### **6.3.2.1 Product Shipment**

The Clinical Logistics Coordinator or designee will contact the Investigator or a designee to determine the dates and times of delivery of products.

Each vaccine shipment will include a temperature-monitoring device to verify maintenance of the cold chain during transit. On delivery of the product to the site, the person in charge of product receipt will follow the instructions given in the Operating Guidelines, including checking that the cold chain was maintained during shipment (ie, verification of the temperature recorders). If there is an indication that the cold chain was broken, this person should immediately quarantine the

product, alert the Sanofi Pasteur representative, and request authorization from Sanofi Pasteur to use the product.

### **6.3.2.2 Product Storage**

The Investigator will be personally responsible for product management or will designate a staff member to assume this responsibility.

At the site, products must be kept in a secure place with restricted access. The Study and Control Products (MenACYW conjugate vaccine or Menveo®) will be stored in a refrigerator at a temperature ranging from +2°C to +8°C and never frozen. All commercially labeled products should be stored according to the manufacturer's instructions. The temperature must be monitored and documented (see the Operating Guidelines) for the entire time that the vaccine is at the study site. In case of accidental freezing or disruption of the cold chain, vaccines must not be administered and must be quarantined, and the Investigator or authorized designee should contact the Sanofi Pasteur representative for further instructions.

### **6.3.2.3 Product Accountability**

The person in charge of product management at the site will maintain records of product delivery to the study site, product inventory at the site, the dose(s) given to each subject, and the disposal of or return to the Sponsor of unused doses.

The necessary information on the product labels is to be entered into the source document and the CRB. If applicable, information may also be entered into the subject's vaccination card.

The Sponsor's monitoring staff will verify the study site's product accountability records against the record of administered doses in the CRBs and the communication from the IRT system.

In case of any expected or potential shortage of product during the study, the Investigator or an authorized designee should alert the Sanofi Pasteur representative as soon as possible, so that a shipment of extra doses can be arranged.

### **6.3.3 Replacement Doses**

If a replacement dose is required (eg, because the vial broke or particulate matter was observed in the syringe), the site personnel must either contact the IRT system to receive the new dose allocation, or follow the instructions given in the Operating Guidelines.

### **6.3.4 Disposal of Unused Products**

Unused or wasted products will be either disposed of or returned to the Sponsor in accordance with the instructions in the Operating Guidelines. Product accountability will be verified throughout the study period.

### **6.3.5 Recall of Products**

If the Sponsor makes a decision to launch a retrieval procedure, the Investigator(s) will be informed of what needs to be done.

## 6.4 Blinding and Code-breaking Procedures

This trial is open-label; therefore, there is no need for code-breaking procedures. Until database lock and to prevent biases, the laboratory personnel performing the serology testing will be blinded to the group assignment. The laboratory will have a written procedure detailing how the blinding will be maintained.

## 6.5 Randomization and Allocation Procedures

On the day of enrollment, subjects who meet the inclusion/exclusion criteria and whose parent / guardian signs the ICF will be randomly assigned in a 2:1 ratio in Mexico, and in a 2:1 ratio in the Russian Federation such that Group 1 will have 200 subjects, Group 2 will have 100 subjects, Group 3 will have 150 subjects, and Group 4 will have 75 subjects.

Site staff will connect to the IRT system, enter the identification and security information, and confirm a minimal amount of data in response to IRT-system prompts. The IRT system will then provide the vaccine assignment and subject number. The full detailed procedures for Group allocation are described in the Operating Guidelines. If a subject who has enrolled is not eligible to participate in the study, then the subject's information will only be recorded on the subject-recruitment log.

Subject numbers that are assigned by the IRT system will consist of a 12-digit string (a 3-digit country identifier, a 4-digit study center identifier, and a 5-digit subject identifier). For example, Subject 840000100005 is the fifth subject enrolled in Center Number 1 in the US (840 being the US country code).

Subject numbers should not be reassigned for any reason. The randomization codes will be kept securely in the IRT system.

## 6.6 Treatment Compliance

The following measures will ensure that the vaccine doses administered comply with those planned, and that any non-compliance is documented so that it can be accounted for in the data analyses:

All vaccinations will be administered by qualified study personnel.

The person in charge of product management at the site will maintain accountability records of product delivery to the study site, product inventory at the site, dose(s) given to each subject, and the disposal of unused or wasted doses.

## 6.7 Concomitant Medications and Other Therapies

At the time of enrollment, ongoing medications including but not limited to other therapies (eg, blood products), should be recorded in the source documents. All new medications prescribed for new medical conditions / AEs during study participation should also be recorded in the source documents.

Documentation in the CRB of concomitant medication(s) will be limited to specific categories of medication(s) (Categories 1, 2, and 3 as detailed below). Those will include Category 1, 2, and 3 medications ongoing at the time of inclusion in the study, or started at any time during the subject's participation in the trial. For category 3 medication, the period of reporting in CRB will be restricted to only 3 days (72 hours) prior to each blood sampling time point.

### **Collection period in source documents**

Reportable medications (Category 1, 2, and 3) will be collected in the source documents from the day of first vaccination to the end of the trial. a

### **Categories of Reportable medications and reporting period**

Reportable medications include medications that impact or may impact the consistency of the safety information collected after any vaccination and/or the immune response to vaccination.

- Category 1: Reportable medications with potential impact on the evaluation of the safety of the study vaccines. For example, antipyretics, analgesics, non-steroidal anti-inflammatory drugs (NSAIDs), systemic corticosteroids (therapy duration less than 2 weeks), and other immune modulators. Category 1 medications do not define the Per-Protocol Analysis Set (PPAS).

*Note: Topical steroids (Inhaled, otic, ophthalmic, nasal etc.) should not be captured or reported.*

Category 1 medications will be reported in the CRB from the day of first vaccination to the end of the solicited and unsolicited follow-up period after each vaccination. These medications will also be collected in the CRB for the 30- day period prior to the subsequent doses of the vaccine, wherever applicable (second, third, fourth, etc., in case of a multi-dose schedule with more than a 30-day interval between doses).

- Category 2: Reportable medications with potential impact on immune response of the study vaccines and used to define the Per-Protocol Analysis Set (PPAS). For example:
  - Flu vaccines administered within 14 days pre or post each trial vaccination, including the day of the study vaccination visit

Any vaccine other than study vaccines (vaccines non-described in the Protocol) within the 28 days (4 weeks) preceding or after the trial vaccination, including the day of the study vaccination visit.

  - Immune globulins, blood or blood-derived products: used in the 3 months preceding the first blood draw and up to the last blood draw
  - Immunosuppressive therapy such as immune-suppressors, immune-modulators with immunosuppressive properties, long-term systemic corticosteroids therapy (prednisone

---

a Subjects/ Subject's parents will be required to document all medications received in the Diary Cards. The sites will focus on only recording the medications belonging to the 3 categories in the other source documents.

or equivalent for more than 2 consecutive weeks) within past 3 months, anti-cancer chemotherapy, anti-proliferative drugs such as DNA synthesis inhibitors, or radiation therapy: used in the 6 months preceding the first trial vaccination, and up to the last blood draw.

Category 2 medications will be reported in the CRB during the study period up to the last blood draw.

- Category 3: Systemic (Oral or injectable) antibiotics, as they may interfere with bioassays used for antibody testing when taken before a blood draw. Antibiotics that the subject received within 72 hours preceding each visit for blood draw related to IMP assessment (meningococcal vaccines) and used to define the PPAS. Category 3 medications will be reported in the CRB for the period of 3 days (72 hours) before each blood draw.

*Note: Topical antibiotics (Inhaled, otic, ophthalmic, nasal, etc.) should not be captured or reported.*

The information reported in the CRB for each reported medication will be limited to:

- Trade name
- Rationale for the origin of prescription: Whether it was a prophylactica medication. Prophylactic medications will be recorded in the Action Taken section of the AE collection tables
- Medication category (1, 2, or 3)
- Start and stop dates
- Dosage and administration route, homeopathic medication, will not be recorded.

If the subject has received medications other than those listed in Categories 1, 2, and 3, the detailed information will be collected in the source documents only.

Medications given to treat an AE will be captured in the “Action Taken” section of the AE CRB only. No details will be recorded in the concomitant medication CRB unless the medication(s) received belongs to one of the prelisted categories.

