#### **12.2.4 Per-Protocol Analysis Set 1 (PPAS1)**

Serology obtained from the last blood sample of infancy vaccination stage for all antigens will be used for immunogenicity analyses of infant stage of the study.

The subjects presenting with at least one of the following relevant protocol deviations during infancy will be excluded from the PPAS1:

- Subject did not meet all protocol-specified inclusion criteria or met at least one of the protocol-specified exclusion criteria
- Subject did not complete the vaccination schedule
- Subject received a vaccine other than the one that he / she was randomized to receive
- Preparation and / or administration of vaccine was not done as per-protocol
- Subject did not receive vaccine in the proper time window, according to the Tables of Study Procedures. All infant stage vaccines (including concomitant vaccines) need to be received as scheduled in the Table of Study Procedures.

- Subject did not provide post-dose serology sample during infancy in the proper time window or a post-dose serology sample was not drawn
- Subject received a protocol-prohibited therapy, medication or vaccine

In addition to the reasons listed above, subjects will also be excluded from the PPAS1 if their infancy post vaccination serology sample did not produce a valid test result (ie, results for all antigens are missing).

In the event of a local or NIC with a pandemic influenza or coronavirus vaccine or any other vaccine as needed, subjects who receive 1 or more doses of the pandemic influenza or coronavirus vaccine at any time during the study will not be withdrawn from the study.

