### 12.2.5 Per-Protocol Analysis Set 2 (PPAS2)

Serology obtained from the last blood sample of 2nd year of life for all antigens will be used for immunogenicity analyses of 2nd year of the study.

The subjects presenting with at least one of the following relevant protocol deviations during 2nd year of life will be excluded from the PPAS2:

- Subject did not meet all protocol-specified inclusion criteria or met at least one of the protocol-specified exclusion criteria
- Subject did not complete the vaccination schedule including the infant and the 2nd year of the study
- Subject received a vaccine other than the one that he / she was randomized to receive during both the infant and 2nd year of the study
- Preparation and / or administration of vaccine was not done as per-protocol during both the infant and 2nd year of the study
- Subject did not receive vaccine in the proper time window. All 2nd year of life vaccines (including concomitant vaccines) need to be received as scheduled in the Table of Study Procedures.
- Subject did not provide post-dose serology sample during infancy in the proper time window or a post-dose serology sample was not drawn during 2nd year of life
- Subject received a protocol-prohibited therapy, medication or vaccine

In addition to the reasons listed above, subjects will also be excluded from the PPAS2 if their 2nd year of life post vaccination serology sample did not produce a valid test result (ie, results for all antigens are missing).

In the event of a local or NIC recommendation or requirement with a pandemic influenza or coronavirus vaccine or any other vaccine as needed, subjects who receive 1 or more doses of the pandemic influenza or coronavirus vaccine at any time during the study will not be withdrawn from the study.

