5.2.1.1 Per-Protocol Analysis Set 1 (PPAS1)

Serology obtained from the last blood sample of infancy vaccination stage for all antigens will be used for immunogenicity analyses of infant stage of the study.

The subjects presenting with at least one of the following relevant protocol deviations during infancy will be excluded from the PPAS1:

- Subject did not meet all protocol-specified inclusion criteria or met at least one of the protocol-specified exclusion criteria
- Subject did not complete the vaccination schedule
- Subject received a vaccine other than the one that he / she was randomized to receive

- Preparation and / or administration of vaccine was not done as per-protocol
- Subject did not receive vaccine in the proper time window, according to the Tables of Study Procedures. All infant stage vaccines (including concomitant vaccines) need to be received as scheduled in the Table of Study Procedures.
- Subject did not provide post-dose serology sample during infancy in the proper time window or a post-dose serology sample was not drawn
- Subject received a protocol-prohibited therapy, medication or vaccine

In addition to the reasons listed above, subjects will also be excluded from the PPAS1 if their infancy post vaccination serology sample did not produce a valid test result (ie, results for all antigens are missing).

In the event of a local or NIC with a pandemic influenza or coronavirus vaccine or any other vaccine as needed, subjects who receive 1 or more doses of the pandemic influenza or coronavirus vaccine at any time during the study will not be withdrawn from the study.

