5.2.4 Populations Used in Analyses

All immunogenicity analyses will be performed on the Per-Protocol Analysis Set (PPAS) including PPAS1 and PPAS2. Additional immunogenicity analyses will be performed for exploratory purposes on the Full Analysis Set (FAS), including FAS1 and FAS2, according to randomization group. All safety analyses will be performed on the Safety Analysis Set (SafAS and SafAS1 – SafAS6).

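### At post-vaccination draws, the 72-hour antibiotic criterion for the PPAS reaches Group 3 but not Group 4, so the two randomised Russian groups face unequal exclusion rules for routine antigens

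*Protocol*

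**What the plan says.** Protocol 6.7 sorts reportable medications into three categories. Category 3 is systemic antibiotics, listed "as they may interfere with bioassays used for antibody testing when taken before a blood draw". The reason given is therefore interference with the assay, not a changed immune response. The criterion covers antibiotics received in the 72 hours before "each visit for blood draw related to IMP assessment (meningococcal vaccines) and used to define the PPAS". Recording is wider: "Category 3 medications will be reported in the CRB for the period of 3 days (72 hours) before each blood draw", with no restriction by group.

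The per-protocol sets are defined by child. For the infant stage, protocol 12.2.4 states: "Serology obtained from the last blood sample of infancy vaccination stage for all antigens will be used for immunogenicity analyses". For the second year, 12.2.5 states: "Serology obtained from the last blood sample of 2nd year of life for all antigens will be used for immunogenicity analyses". SAP 5.2.4 adds: "All immunogenicity analyses will be performed on the Per-Protocol Analysis Set (PPAS) including PPAS1 and PPAS2". That includes the routine-vaccine endpoints of secondary objective 3.

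Neither PPAS exclusion list names antibiotics. The nearest item, in SAP 5.2.1.1 and again in 5.2.1.2, is "Subject received a protocol-prohibited therapy, medication or vaccine". Elsewhere the SAP mentions antibiotics only in footnotes to the study procedure tables.

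**The concern.** Groups 3 and 4 are the trial's only randomised contrast of routine vaccines given with and without MenACYW, and protocol 5.1.2 gives interference with routine vaccination as a central reason for the design. For that contrast to be read at face value, children should leave the analysis set under the same rules in both groups.

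A criterion tied to meningococcal draws can operate in only one of the two. Recent antibiotic use also goes with recent illness, so the children removed are unlikely to be a random sample. Group 3's routine-antigen results would describe children free of recent antibiotics, while Group 4's would describe all comers.

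**Working it through.** The plan states no figure on this point to reproduce. The check sets the provisions side by side and then sizes the effect under stated assumptions.

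**Which draws and groups the criterion reaches**

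1. Protocol 9.1.1.2 assigns hSBA to Groups 1, 2 and 3. Protocol 9.2.1.2 assigns rSBA to subsets of the same three groups. Neither Table 5.4 nor the titration priorities in 9.2.1.2 give Group 4 any meningococcal assay. Group 4 therefore has no draw that meets the Category 3 condition.
2. First draw (BL0001): exclusion criterion 20 bars antibiotic use within 72 hours in all groups, and an eligibility breach is a PPAS exclusion in all groups. The rules are equal here.
3. BL0002: the footnotes to the procedure tables for Groups 3 and 4 are the same. The draw is postponed within its window if possible; otherwise it is taken and the exposure documented. Some exposed samples are thus expected in both groups.
4. BL0003: the postponement footnote names only the second draw, so it does not reduce exposure here.
5. At BL0002 and BL0003, then, the text gives a PPAS criterion for Group 3 and none for Group 4. Because each PPAS covers all antigens, the Group 3 child would lose DTP, polio, PRP and hepatitis B results (BL0002) or MMR results (BL0003) from the PPAS.
6. Groups 1 and 2 both have meningococcal testing, so the criterion treats them alike.

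**Size**

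Inputs from the documents: Group 3 n = 150, Group 4 n = 75 (protocol 6.5).

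Assumed inputs: *a*, the share of children exposed within 72 hours of a post-vaccination draw; *d*, the difference in response percentage between exposed and unexposed children.

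Expected exclusions = n × *a*. If Group 3 keeps only unexposed children (response *p*) and Group 4 keeps everyone (response *p* − *a* × *d*), the artefactual difference is *a* × *d*.

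| *a* | Group 3 excluded (150 × *a*) | Group 4 excluded, as written | Group 4 excluded under a common child-level rule (75 × *a*) | *a* × *d* for *d* = 5 to 20 points |
|---|---|---|---|---|
| 1% | 1.5 | 0 | 0.75 | 0.05 to 0.2 |
| 3% | 4.5 | 0 | 2.25 | 0.15 to 0.6 |
| 5% | 7.5 | 0 | 3.75 | 0.25 to 1.0 |
| 10% | 15 | 0 | 7.5 | 0.5 to 2.0 |

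The Group 3 counts are upper figures for BL0002, where postponement will clear some exposures.

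For scale, 95% Clopper-Pearson intervals at about 95% response are 86.9% to 98.5% for 71/75 and 89.8% to 97.7% for 142/150. An artefact of 0.05 to 2.0 points is small beside either.

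**The case against.** The strongest reply is that removal of the child is inferred. Antibiotics appear in neither PPAS list, nothing prohibits them during follow-up, and sites are told to draw and document when a delay would miss the window. Saying that Category 3 helps define the PPAS does not say whether the child, the sample or the assay result is dropped. No text says that exposed Group 4 children are kept, and the Visit 5 antibiotic check and the recording of Category 3 use apply to both Russian groups.

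This is fair, and it is why the point is put as the literal reading. It does not remove the problem. Protocol 6.7 says outright that Category 3 defines the PPAS, limits it to meningococcal draws, and leaves the PPAS definitions with no level below the child. Either the provision operates and the groups differ, or the SAP has dropped it without saying so.

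Three further replies stand in full:

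- FAS1 and FAS2 keep these children in every group, so a symmetric analysis exists, although it is exploratory.
- All analyses are descriptive, and the specified outputs are summaries by group with no planned Group 3 minus Group 4 difference. No test or power statement changes.
- A reader might infer that the interference is confined to the bactericidal assays. The documents do not say so: they refer to bioassays generally, and polio is measured by cell-culture neutralization (protocol 9.2.1.2). Whether polio results are affected is for the laboratory to say.

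**Conclusion.** The point holds in limited form. At BL0002 and BL0003, the text as written applies an antibiotic criterion to Group 3's routine-antigen results that it does not apply to Group 4's, and the SAP does not resolve this. With 1-5% exposure assumed, the imbalance is at most about 1.5-7.5 of 150 against 0 of 75 per draw. Widening the assumptions to 1-10% exposure and a 5-20 point response difference gives an artefact of 0.05 to 2.0 percentage points. No planned conclusion turns on that. The case for acting is that a stated rule treats two randomised groups differently according to recent illness, and correcting it is cheap.

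Two stronger readings are not supported. A reader might infer that Group 4 children are never removed for antibiotic use; criterion 20 removes them at the first draw. A reader might also infer that the Mexican results are biased or lost. Groups 1 and 2 are treated alike, and their results remain in the FAS. What Mexico loses is some PPAS precision on routine antigens: at 1-5% exposure, up to 2-10 of 200 in Group 1 (200 × 1-5%) and 1-5 of 100 in Group 2 (100 × 1-5%) per draw.

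**What to change.** In SAP 5.2.1.1 and 5.2.1.2, and in protocol 6.7, 12.2.4 and 12.2.5, state one rule for all four groups:

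- Systemic antibiotics within 72 hours of a post-vaccination draw make only the hSBA and rSBA results of that sample non-evaluable in the PPAS.
- The same applies to any other assay that the laboratory confirms is affected, polio neutralization being the one to ask about, with the flag set identically in Groups 3 and 4.
- The child stays in the PPAS for all other antigens.
- The number flagged is reported by group and draw.

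The cost is wording, one programming flag and slightly different denominators by antigen. No new data are needed, because Category 3 use is already recorded before every draw in every group. SAP 5.7 makes the data in the first analysis step final, so the rule should be fixed before that lock.
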